9. DATA COLLECTION

All the data will be collected based on a series of variables which derive from an accurate narrative review of the UI predictors, costs and quality of life of the women affected by the problem (Danforth et al., 2006; Datar et al., 2022; Goren et al., 2014; Harding et al., 2023; Sensoy et al., 2013). These variables are described in Table 1. The obtained information will be gathered in the eCRF, which the investigators will only access during the analyses and synthesis of data.

Table 1 - Outcome and description of the investigated variables

OUTCOME	VARIABLE	DESCRIPTION
UI predictors	Age	The prevalence of UI seems strongly related to the age of the woman and specifically prevalence figures increase with increasing age (Milsom & Gyhagen, 2019)

	Ethnicity	The risk of SUI appears to be lower in black and Asian-American women compared to white women (Danforth et al., 2006; Thom et al., 2006)
	Scholarship	According to some studies (Batmani et al., 2021; Marques et al., 2015), increasing the level of education is an important factor in reducing the incidence of urinary incontinence
	Body Mass Index (BMI)	There is evidence that the prevalence of both UUI and SUI increases proportionately with BMI (Harding et al., 2023)
	Comorbidities	
Lower urinary tract symptoms are associated with multiple comorbid conditions including:
 
 • cardiac failure • chronic renal failure • chronic obstructive pulmonary disease • diabetes • hypertension • metabolic syndrome • pelvic organs prolapse • urinary tract infections • bowel disorders (constipation, irritable bowel syndrome) • sleep disturbances • depression • neurological disease • general cognitive impairment 
(Batmani et al., 2021; Harding et al., 2023; Sensoy et al., 2013; Wang et al., 2010)

	Pelvic or uro-gynecological surgery	Other factors positively associated with SUI include previous pelvic or uro-gynecological surgery (Ellström Engh et al., 2006; Harding et al., 2023)

	Menopause	Menopausal status seems to influence the onset and characteristics of urine leakage (Sensoy et al., 2013; Thangarajah et al., 2020)
	Parity	Pregnancy and childbirth are triggers for SUI (Li et al., 2023; Bortolotti et al., 2000)
UI prevalence and symptomatology	Lifestyle factors	
 Unhealthy voiding behavior (Hu and Pierre, 2019) and low physical activity may contribute to UUI onset (Li et al., 2023) Smoking cessation is a general public health measure and has been shown to be weakly associated with improving urgency, frequency and UI (Danforth et al., 2006; Harding et al., 2023) Decrease in fluid intake may improve some symptoms in patients with SUI and idiopathic detrusor overactivity (Swithinbank et al., 2005) Reduction of caffeine intake may reduce symptoms of frequency and urgency (Harding et al., 2023) An association was seen between alcohol consumption and urinary incontinence in middle-aged and older women (Lee & Hirayama, 2012)
	Frequency of urine leakage	To assess the severity of UI among female, we need measuring the “frequency” and “usual amount” of leakage ranged from “moderate” to “strong” (Avery et al., 2004)
	Perceived quantity of urine leakage	
	Type of urine leakage	It is focused on subtypes of urinary incontinence (SUI, UUI and MUI) (Abrams et al., 2003)
	Time of onset of urine leakage	The mean age in which urine leakage begins seems to be lower for SUI compared to MUI and UUI (Thangarajah et al., 2020)

 
I.R.C.C.S. Ospedale San Raffaele
	
STUDY PROTOCOL
	
WUIPS Version n. 1 23.08.2023

---	------------------------------	---

UI quality of life, social impact	General interference with daily life	The measurement of UI should incorporate the impact that the condition may have on quality of life (Avery et al., 2004)
	Interference with specifical activities	
Specifically:
 
 • Physical Activity • Social Relationships • Travel • Emotional Health 
(Monticone et al., 2021; Shumaker et al., 1994)

	Interference with sexual life	Some articles report that UI affects sexual aspects of the individual (Felsted & Supiano, 2019; Marques et al., 2015). According to other studies, sexual activity does not seem to be damaged by UI (Siracusano et al., 2003)
Costs	Work productivity	UI imposes a high economic burden because of work productivity loss (Goren et al., 2014)
	Weekly costs of hygiene care products	UI is associated with substantial routine care “costs” (Subak et al., 2006)
	Healthcare resource utilization: 1. Specialist visits 2. Treatments	Women with SUI/MUI consume significantly higher medical resources and incur higher costs to payers, compared to women without SUI/MUI (Datar et al., 2022)

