7. INCLUSION/EXCLUSION CRITERIA

7.1 Inclusion criteria

- Female sex
- Middle age (40-65 years old)
- Informed consent signed
- Comprehension of written and spoken Italian language
- Female outpatients intended for any hospital unit (outpatient clinic, day surgery and day hospital patients included) and every female caregiver respecting the previous inclusion criteria, recruited at the central admission and at the private admission of the four hospitals involved
- Female workers (healthcare professionals and administrative personnel) of the four hospitals

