9.1 Instruments

Three instruments will be employed to collect data, as reported in Table 2.

 I.R.C.C.S. Ospedale San Raffaele	STUDY PROTOCOL	WUIPS Version n. 1 23.08.2023
--	-----------------------	--

Table 2 - Instruments employed in the study

Instrument	Data of interests
UI Survey	Women's socio-demographic and clinical characteristics based on the variables reported in Table 1
Italian version of the International Consultation of Incontinence Modular Questionnaire Urinary Incontinence Short Form (ICIQ UI-SF) (Tubaro et al., 2006)	Prevalence and symptomatology of UI (Bedretdinova et al., 2015)
Italian version of the Incontinence Impact Questionnaire-7 (IIQ-7) (Monticone et al., 2020)	Impact on life of urinary incontinence among women (Shumaker et al., 1994)

A survey, written in Italian by the authors and tested on a sample of 13 women between 40 and 65 years old, will collect socio-demographic, economic and clinical characteristics of all the female participants included in the study. The requested data will be based on the variables reported in Table 1.

The Italian version of the International Consultation of Incontinence Modular Questionnaire Urinary Incontinence Short Form (ICIQ UI-SF) will be used to investigate UI symptoms in women (Avery et al., 2004; Tubaro et al., 2006).

The Italian version of the Incontinence Impact Questionnaire-7 will be used to assess the impact of UI on women's quality of life (Monticone et al., 2021; Shumaker et al., 1994).

The materials necessary for data collection will be included in a paper module for patients and caregivers and online for staff (see attachment). Each subject included will fill in the module which will be transmitted to the Promoter with the appropriately anonymized data. Given the growing need for digital data management in clinical trials and in compliance with current regulatory requirements, researchers will independently set up the eCRF (electronic Case Report Form), via the RedCap platform.

In each hospital center involved in the study, a nurse will be identified, as the contact person of the Center, who will be responsible for supervising the appropriate recording of data and compliance with this research protocol.

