9.1.1 UI Survey

A survey, written in Italian by the authors, will collect women's socio-demographic, economic and clinical characteristics, based on the variables reported in Table 1. The entire survey is attached in Appendix.

 
I.R.C.C.S. Ospedale San Raffaele
	
STUDY PROTOCOL
	
WUIPS Version n. 1 23.08.2023

---	------------------------------	---

A total of 29 questions will attempt to acquire information about some of the previously defined variables: specifically, 23 questions will be related to socio-demographic and clinical predictors of UI (n. 1-23), one question will be about the onset of the UI symptomatology (n. 35), one question about sexuality (n. 36) and four questions will investigate the direct and indirect costs of UI (n. 37-40). The survey was tested as a pilot on a sample of 13 women aged between 40 and 65 years old and was assessed as suitable for the following aspects: understanding and clarity of the questions, absence of questions that put the participant in difficulty, completion time (which resulted maximum of 5 minutes).

9.1.2 International Consultation of Incontinence Modular Questionnaire Urinary Incontinence Short Form (ICIQ UI-SF)

The International Consultation of Incontinence Modular Questionnaire Urinary Incontinence Short Form (ICIQ UI-SF) is a questionnaire that allows the assessment of the prevalence, frequency, and perceived cause of UI and its impact on everyday life. It is an appropriate scale for estimating national prevalence in representative samples (Bedretdinova et al., 2015).

ICIQ UI-SF was developed and validated in English for the first time by Avery and colleagues in 2004, and then Tubaro and colleagues made an Italian Validation in 2006. This last version will be used in the study.

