APPENDIX

UI SURVEY – SCHEDA di RACCOLTA DATI

Gentilissima, nel ringraziarla per aver accettato di contribuire a questa ricerca, la invitiamo a rispondere alle domande di seguito, di natura clinica e socio-demografica, con le quali indaghiamo alcuni fattori che potrebbero essere predisponenti all'insorgenza di una condizione nota come incontinenza urinaria.

1. Indichi il suo anno di nascita:

--	--	--	--

2. Indichi la sua nazionalità:

1. Italiana
 2. Straniera (specificare _____)

3. Indichi la regione di domicilio:

- 1. Lombardia
- 2. Altra regione (specificare _____)

4. Se è domiciliata in Lombardia, indichi la provincia del suo domicilio:

 1. Bergamo	 5. Lecco	 9. Monza
 2. Brescia	 6. Lodi	 10. Pavia
 3. Como	 7. Mantova	 11. Sondrio
 4. Cremona	 8. Milano	 12. Varese

5. Indichi il suo peso in chili:

--	--	--

6. Indichila sua altezza in centimetri

10 cm

7. Indichi il grado massimo di studi raggiunto (scolarità):

- 1. Educazione primaria (elementari, medie)
- 2. Educazione secondaria o avanzata (diploma di istituto professionale, tecnico o liceo, laurea)

8. Soffre o ha mai sofferto di una delle seguenti patologie? (Può indicare anche più di una risposta):

- 1. Insufficienza cardiaca
- 2. Insufficienza renale cronica
- 3. Broncopneumopatia cronico-ostruttiva (BPCO)

- 4. Diabete
- 5. Ipertensione
- 6. Sindrome metabolica
- 7. Prollasso vescicale / vaginale / rettale
- 8. Infezione ricorrente delle vie urinarie
- 9. Sindrome da intestino irritabile
- 10. Stipsi
- 11. Disturbi del sonno
- 12. Depressione
- 13. Patologia neurologica
- 14. Disabilità cognitiva generale
- 14. Altro (specificare: _____)

9. Ha mai subito interventi di chirurgia ginecologica e/o urologica?

- 1. Sì
- 2. No

10. Se alla domanda precedente ha risposto Sì, specifichi quale/i intervento/i ha subito:

11. In quale stato menopausale si definirebbe?

- 1. In pre-menopausa
- 2. A inizio menopausa
- 3. In post-menopausa

12. Ha figli?

- 1. Sì
- 2. No

13. Se alla domanda precedente ha risposto Sì, indichi il numero di figli:

- 1
- 2
- ≥ 3

14. Indichi l'anno di nascita dell'ultimo figlio

--	--	--	--

15. Quanti parto per via vaginale ha avuto?

- 0
- 1
- 2
- ≥ 3

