- 5. Ho perdite di urina quando sono in movimento e durante l'attività fisica
- 6. Ho perdite di urina quando ho finito di urinare e mi sono rivestita
- 7. Ho perdite di urina senza ragioni particolari
- 8. Ho perdite di urina continuamente

Incontinence Impact Questionnaire-7 (Italian)

Le saremmo grati se rispondesse a queste ultime domande, per comprendere l'influenza sulla qualità di vita delle perdite di urina che ha riscontrato.

NOTA BENE: Se non ha mai riscontrato perdite di urina, le chiediamo di apporre una crocetta sul seguente quadratino e di non rispondere alle domande nella tabella. Grazie per la collaborazione.

- Non ho perdite di urina

Se ha riscontrato perdite di urine, queste perdite hanno influenzato...

	Per nulla	Molto poco	Un po'	Molto
28. La sua capacità di fare le faccende domestiche (cucina, pulizie di casa, lavanderia, ecc.)?	0	1	2	3
29. Le sue attività fisiche ricreative, come camminare, nuotare, o fare	0	1	2	3

altro esercizio?				
30. Le sue attività del tempo libero (andare al cinema, concerti, ecc.)?	0	1	2	3
31. La sua capacità di viaggiare in auto o in autobus per più di 30 minuti da casa?	0	1	2	3
32. La sua partecipazione ad attività sociali fuori casa?	0	1	2	3
33. La sua salute emotiva (nervosismo, depressione, ecc.)?	0	1	2	3
34. I suoi sentimenti di frustrazione?	0	1	2	3

Di seguito le poniamo qualche domanda su insorgenza, evoluzione, impatto della patologia e costi da essa derivanti.

NOTA BENE: Se non ha mai riscontrato perdite di urina, le chiediamo di apporre una crocetta sul seguente quadratino e di non rispondere alle domande successive. Grazie per la collaborazione.

Non ho perdite di urina

35. Da quanto tempo ha delle perdite di urina?

- 1. Da 1 anno o meno
- 2. Da 2-5 anni
- 3. Da 6-10 anni
- 4. Da più di 10 anni

36. Le sue perdite di urina hanno influenzato la sua vita sessuale?

- 1. Per nulla
- 2. Molto poco
- 3. Un po'
- 4. Molto

37. Le sue perdite di urina hanno comportato assenteismo o minore produttività sul posto di lavoro?

- 1. No
- 2. Sì, raramente
- 3. Sì, a volte
- 4. Sì, spesso

38. In media, potrebbe fornire una stima della spesa settimanale che sostiene per l'acquisto di prodotti igienici specifici per le perdite di urina (assorbenti o pannolini, salviettine, detergenti intimi specifici, ecc.)?

- 1. Non acquisto alcun prodotto specifico per le perdite di urina
- 2. Spendono meno di 3 euro a settimana
- 3. Spendono fino a 5 euro a settimana

- 4. Spendò tra i 6 e i 10 euro a settimana

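### Ethnicity is a listed predictor but the form records only nationality, and question 37 cannot separate women who do not work from workers with no productivity loss

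*Protocol*

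**What the plan says.** **Ethnicity.** Table 1 in Protocol section 9 names ethnicity among the predictors and justifies it thus: "The risk of SUI appears to be lower in black and Asian-American women compared to white women". Section 9.1 says of the survey: "The requested data will be based on the variables reported in Table 1". Section 9.1.1 states that "23 questions will be related to socio-demographic and clinical predictors of UI (n. 1-23". In the Appendix, the only related item in that block is question 2, "Indichi la sua nazionalità", answered as Italian or as foreign with a free-text field.

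**Work productivity.** Table 1 places work productivity under costs, on the ground that "UI imposes a high economic burden because of work productivity loss". The form measures it with question 37 alone: "Le sue perdite di urina hanno comportato assenteismo o minore produttività sul posto di lavoro". The four answers are no; yes, rarely; yes, sometimes; yes, often. Just before question 35, a woman who has never had leakage is asked "di apporre una crocetta sul seguente quadratino e di non rispondere alle domande successive". No other skip applies to questions 35 to 40.

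**Who answers.** Section 7.1 admits outpatients and "every female caregiver respecting the previous inclusion criteria", with no condition on employment, as well as female staff of the four hospitals. Section 4 makes the description of predictors and costs, and their association with incontinence, secondary outcomes.

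**The concern.** The two gaps are separate but of one kind: the form does not collect what Table 1 says will be studied.

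Nationality is not ethnicity. It cannot place an Italian national in any ethnic group, so the contrast that justifies the predictor cannot be examined.

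A woman with leakage who has no job is directed to question 37 and finds only one answer that fits, *No*. Her *No* then reads like that of an employed woman who lost nothing. If she leaves the item blank, it reads like ordinary non-response. Among patients and caregivers, the share of workers with productivity loss therefore has no usable denominator. The share among all women with incontinence is right only if every non-worker ticks *No*, which the form does not tell her to do.

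Staff are all employed, while patients and caregivers are a mix of unknown composition. A difference between the two groups on question 37 could therefore come from employment alone.

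**Working it through.** **Step 1. Match Table 1 to the collection tools.**

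- Ethnicity: questions 1 to 23 contain nationality (question 2) but no ethnic group. Questions 24 to 27 (ICIQ UI-SF), 28 to 34 (IIQ-7) and 35 to 40 contain nothing relevant. The recruitment interview in section 8 covers age, pregnancy or puerperium, and past gynaecological surgery. The variable is absent.
- Work productivity: question 37 only. No item from 1 to 40 asks about occupation or employment, and neither does the interview. The number of workers is known for staff, who are employed by definition, but not for patients and caregivers.

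**Step 2. Illustrate the effect on question 37.** The Protocol has no figure to reproduce and gives no employment data, so every input here is an assumption. Among patients and caregivers with incontinence, let

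- p = true share of workers with some loss, taken as 20%;
- w = share not working, taken as 10%, 30% or 50%;
- b = share of non-workers who leave question 37 blank; the others tick *No*.

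All workers are taken to answer. Then

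- share reported among those answering = p(1 − w) / (1 − wb);
- share among workers = p;
- share among all women with incontinence = p(1 − w).

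| | w = 10% | w = 30% | w = 50% |
|---|---|---|---|
| Target, workers | 20% | 20% | 20% |
| Target, all women with incontinence | 18% | 14% | 10% |
| Reported, b = 0 | 18.0% | 14.0% | 10.0% |
| Reported, b = 0.5 | 18.9% | 16.5% | 13.3% |
| Reported, b = 1 | 20.0% | 20.0% | 20.0% |

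For example, with w = 30% and b = 0.5: 0.20 × 0.70 / (1 − 0.15) = 0.14 / 0.85 = 16.5%.

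With b = 0 the form gives the all-women share and falls 2, 6 or 10 points below the workers' share. With b = 1 it gives the workers' share and lies 2, 6 or 10 points above the all-women share. With b = 0.5 it matches neither: 1.1, 3.5 or 6.7 points below the first and 0.9, 2.5 or 3.3 points above the second.

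**Step 3. Read it in reverse.** Suppose 14% is observed and w may lie anywhere from 0 to 50%.

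- If non-workers ticked *No*, the workers' share is 14% / (1 − w): 14.0%, 15.6%, 20.0% and 28.0% at w = 0, 10%, 30% and 50%.
- If non-workers left it blank, the all-women share is 14% × (1 − w): 14.0%, 12.6%, 9.8% and 7.0%.

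The completed forms hold nothing that would choose among these readings.

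**The case against.** The strongest reply is that the Protocol never promises a figure among workers. Sections 4 and 5 speak of the costs of women with incontinence. On that reading a non-worker's *No* is true, and a form completed as instructed gives an unbiased share. This stands, and the b = 0 row shows it. It depends, however, on every non-worker ticking *No* to a question about her workplace, and a workers-only figure remains out of reach.

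The choice of denominator could also be left to a statistical analysis plan. That is fair, and its absence here is not the point. No analysis plan can recover a variable that the form does not collect.

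The sizes are assumed, and nothing in the Protocol shows how many non-workers would leave the item blank. Both are true. The effect is also confined to patients and caregivers. Staff data arrive separately and can be reported alone, and section 11 counts 1,842 female employees aged 40 to 65 at two of the hospitals, so a pooled figure would be distorted less.

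Paper forms carry a number and are handed back on the spot, so a blank might be queried then. A non-worker's *No* would prompt no query, and sections 8 and 16 describe the data as anonymous, with section 16 adding that they cannot be traced to an individual.

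On ethnicity, section 9.1.1 says the survey covers only some of the variables. The other two questionnaires do not supply this one. The free-text nationality field is at best a crude proxy. The pilot in 13 women checked clarity, ease and completion time, not agreement with Table 1.

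**Conclusion.** Both parts hold. Ethnicity, as Table 1 defines it, is not measured and cannot be reported as a predictor. For patients and caregivers, productivity loss among workers cannot be computed, and the share among all women with incontinence is secure only if non-workers uniformly answer *No*. Under the assumed 20% loss with 10% to 50% not working, the reported figure may miss one target or the other by up to 10 points. These sizes illustrate the problem and do not estimate it.

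The reach is limited. Only secondary outcomes are touched; the primary prevalence estimate and the staff results for question 37 are sound, and the count of women answering *Yes* can still be reported. The point is worth acting on because the correction is nearly free before launch and the information cannot be recovered from anonymous forms afterwards.

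**What to change.** Before launch:

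1. Add *I do not work* to question 37. Report productivity loss among workers, and state beside it how many women were not working. The all-women share then follows from the same answers.
2. Either rename the Table 1 predictor nationality, replace its rationale and make no claim about ethnicity, or add a self-declared ethnicity item with a *prefer not to answer* option.

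The cost is one answer option, plus one relabelled row or one added item. Both changes fall in the researcher-built survey, so the validated ICIQ UI-SF and IIQ-7 are untouched. The form becomes slightly longer. An ethnicity item would collect sensitive data, which relabelling avoids.

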9.1 Instruments

Three instruments will be employed to collect data, as reported in Table 2.

 I.R.C.C.S. Ospedale San Raffaele	STUDY PROTOCOL	WUIPS Version n. 1 23.08.2023
--	-----------------------	--

Table 2 - Instruments employed in the study

Instrument	Data of interests
UI Survey	Women's socio-demographic and clinical characteristics based on the variables reported in Table 1
Italian version of the International Consultation of Incontinence Modular Questionnaire Urinary Incontinence Short Form (ICIQ UI-SF) (Tubaro et al., 2006)	Prevalence and symptomatology of UI (Bedretdinova et al., 2015)
Italian version of the Incontinence Impact Questionnaire-7 (IIQ-7) (Monticone et al., 2020)	Impact on life of urinary incontinence among women (Shumaker et al., 1994)

A survey, written in Italian by the authors and tested on a sample of 13 women between 40 and 65 years old, will collect socio-demographic, economic and clinical characteristics of all the female participants included in the study. The requested data will be based on the variables reported in Table 1.

The Italian version of the International Consultation of Incontinence Modular Questionnaire Urinary Incontinence Short Form (ICIQ UI-SF) will be used to investigate UI symptoms in women (Avery et al., 2004; Tubaro et al., 2006).

The Italian version of the Incontinence Impact Questionnaire-7 will be used to assess the impact of UI on women's quality of life (Monticone et al., 2021; Shumaker et al., 1994).

The materials necessary for data collection will be included in a paper module for patients and caregivers and online for staff (see attachment). Each subject included will fill in the module which will be transmitted to the Promoter with the appropriately anonymized data. Given the growing need for digital data management in clinical trials and in compliance with current regulatory requirements, researchers will independently set up the eCRF (electronic Case Report Form), via the RedCap platform.

In each hospital center involved in the study, a nurse will be identified, as the contact person of the Center, who will be responsible for supervising the appropriate recording of data and compliance with this research protocol.

